4.3 SECONDARY ENDPOINTS

The secondary endpoints are as follow:

- 1. Freedom from AF/AT after one or two procedures at 12 months following index procedure.
- 2. Freedom from AF/AT after a single procedure at 12 months following index procedure.
- 3. The safety endpoint is a composite endpoint, the events of which it is comprised include that of death, cerebrovascular event, or serious treatment-related adverse event at the 12-month timepoint since initial index procedure (this endpoint is inclusive of the Blanking Period marked by the 3 months immediately following the initial index procedure undergone by each enrolled subject).

4.3.1 Secondary Analysis

The secondary endpoint analyses will consist of the following:

Two tests of the primary endpoint in the mITT population, but expanded to be defined as freedom from AF/AT, with or without AADs, 12 months after one or two procedures. A superiority hypothesis will be tested using a Cox proportional hazards model with randomization group, AF duration, and AF/AT strata as fixed effects, with a one-sided alpha level of 0.025:

Both analyses under will be evaluated according to the following hypotheses:

$$H_0$$
: $S_1(t) = S_2(t)$

$$H_A$$
: $S_1(t) > S_2(t)$,

where $S_1(t)$ and $S_2(t)$ represent the survival functions for the Tailored and Anatomical arms, respectively, at any given time t. If the null hypotheses for each of the tests is rejected, the following superiority statements will be considered on behalf of each endpoint:

- 1. Tailored ablation is superior to anatomical with respect to freedom from AF/AT, with or without AADs, 12 months after one or two procedures.
- 2. Tailored ablation is superior to anatomical with respect to freedom from AF/AT, with or without AADs, 12 months after one procedure.

Similarly to the primary endpoint analyses, Cox Proportional hazards regression models will be fit and assessed for goodness-of-fit. Then to test each null hypothesis, one-sided Log-Rank Tests will be. Just like under the primary analysis, the p-value from the one-sided Log-Rank Test run under each Cox Proportional hazards model will ultimately be what is used to either reject (p < 0.025) or fail to reject ($p \ge 0.025$) the null hypotheses above. Both Cox models will be conducted in the mITT population.

Kaplan-Meier plots will be generated for each endpoint, to visually display the differences among the survival distributions of the Tailored and Anatomical arms, respectively, with each plot accommodated by the p-value generated from their respective one-sided Log-Rank test.

3. The composite adverse event (AE) rate defined as the number of AEs per month occurring in each treatment arm from time of index procedure through to 12-month follow-up, where composite AEs are defined by either death, a cerebrovascular event, or any serious procedure-related adverse event, will be conducted. in the Safety population (see Section 4.5, Safety Endpoints below).

4.3.2 Sensitivity Analyses of Secondary Survival Endpoints

The first two Secondary Endpoint Analyses will additionally be conducted in the PP population.

4.4 EXPLORATORY ENDPOINTS

The following endpoints compared in anatomical vs. tailored groups will be considered exploratory:

- 1. Freedom from documented AF, after one or two procedures, with or without AADs, at 12 months
- 2. Freedom from documented AF or AF/AT, after one procedure, or one procedure or more, without AADs, at 12 months
- 3. Freedom from documented AF or AF/AT, after one procedure, or one procedure or more, without AADs or with previously failed AAD at the same dose, at 12 months
- 4. Freedom from documented AF or AF/AT, after one procedure, or one procedure or more, with or without AADs, at 12 months, without the use of TTM
- 5. Freedom from documented symptomatic AF or AF/AT, after one procedure, or one procedure or more, with or without AADs, at 12 months
- 6. Freedom from AF or AF/AT, with or without AADs, 12 months after one procedure, or one procedure or more, for subjects with persistent AF <1 year.
- 7. Freedom from AF or AF/AT, with or without AADs, 12 months after one procedure, or one procedure or more, for subjects with AF ≥ 6 months (including long-standing persistent AF)
- 8. Estimated AF or AF/AT burden, with or without AADs, after one procedure, or one procedure or more
- 9. Quality of life measurements (SF-36 and AFEQT) at baseline, 3, 6 and 12 months post-index procedure
- 10. Incidence of peri-procedural complications including stroke, PV stenosis, cardiac perforation, esophageal injury, and death
- 11. Acute AF termination rate by ablation
- 12. Rate of conversion to sinus rhythm by ablation
- 13. Ablation procedure duration
- 14. Fluoroscopy time and dose
- 15. Mapping time
- 16. Radiofrequency (RF) time to terminate AF
- 17. Total RF time
- 18. Total delivered energy (mean power x RF duration)
- 19. Total delivered energy (mean power x RF duration) / biatrial surface
- 20. Ablation surface area to terminate AF
- 21. Total ablation surface area
- 22. Blinded baseline Voltage maps before ablation
- 23. TTM compliance (% of transmissions expected vs received at each week post index procedure)

4.4.1 Exploratory Endpoint Analysis

Endpoints 1-8 will be tested using a Cox proportional hazards model with randomization group and AF strata as fixed effects. Hypotheses will be tested in the following order, and each at a less stringent one-sided alpha level of 0.05, given the exploratory nature of these analyses)

Endpoint 9 will be tested by comparing the QoL score at each visit between tailored and anatomical ablation using a t-test for difference in means. A Shapiro-Wilks test will be used to assess whether the data meets normality assumptions for parametric. Should the normality assumption be violated, a non-parametric method such as the Wilcoxon test will be used instead. The effect of time will also be assessed using a generalized linear mixed model for repeated measures.

Endpoints 10 - 21 and 23 will be tested by comparing tailored and anatomical ablation groups. using a t-test for differences in means. Should the normality assumption be violated, a non-parametric method such as the Wilcoxon test will be used instead.

Endpoint 22 will not undergo any statistical analysis, but the data collected (blinded baseline voltage maps prior to ablation) will be provided to the sponsor in a dataset / spreadsheet format to enable any post-hoc analysis that may be desired.

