#### 4.3 – Other exploratory endpoints

Exploratory endpoints are defined in Table 4 below.

Table 4: Exploratory endpoints

Endpoint	Description
Other long-term effectiveness endpoints	
5. Freedom from documented AF, after one or two procedures, with or without AADs, at 12 months
 
6. Freedom from documented AF or AF/AT, after one procedure, or one procedure or more, without AADs, at 12 months*
 
7. Freedom from documented AF or AF/AT, after one procedure, or one procedure or more, without AADs or with previously failed AAD at the same dose, at 12 months**
 
8. Freedom from documented AF or AF/AT, after one procedure, or one procedure or more, with or without AADs, at 12 months, without the use of TTM†
 
9. Freedom from documented symptomatic AF or AF/AT, after one procedure, or one procedure or more, with or without AADs, at 12 months‡
 
10. Freedom from AF or AF/AT, with or without AADs, 12 months after one procedure, or one procedure or more, for subjects with persistent AF <1 year
 
11. Freedom from AF or AF/AT, with or without AADs, 12 months after one procedure, or one procedure or more, for subjects with AF ≥ 6 months (including long-standing persistent AF)
 
12. Estimated AF or AF/AT burden#, with or without AADs, after one procedure, or one procedure or more
 
*Primary and secondary endpoints 1-4 with no AAD after the blanking period  **Primary and secondary endpoints 1-4 with no AAD after the blanking period or with previously failed AAD at the same dose  †Primary and secondary endpoints 1-4 with limited non-invasive monitoring (Holters and 12-lead ECG only)  ‡Primary and secondary endpoints 1-4 considering only documented episodes for which the patient was symptomatic, based on patient declaration (e.g. through TTM recordings annotation) and Quality-Of-Life questionnaire results  #Post-ablation arrhythmia burden is estimated based on TTM and/or Holter recordings

Quality of Life	13. QoL measurements (SF-36 and AFEQT) at baseline, 3, 6 and 12 months post-index procedure
Acute safety endpoint	14. Incidence of peri-procedural complications including stroke, PV stenosis, cardiac perforation, esophageal injury, and death
Acute effectiveness endpoints	
15. AF termination rate by ablation*
 
16. Rate of conversion to sinus rhythm by ablation*
 
*Correlation between acute effectiveness and long-term effectiveness will be assessed in both arms

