#### 5.3.5 – Trans Telephonic event Monitor (TTM)

All patients will receive a portable ECG device (KardiaMobile, AliveCor) that they will keep throughout their participation in the Study. They will be asked to perform one 30-second ECG recording per week, and whenever they have arrhythmia symptoms. All TTM recordings will be automatically uploaded in a secured platform for blind review by the ECG core lab.

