#### 5.3.6 – Follow-up period

All patients will be followed-up for 12 months with scheduled in-office visits at 3, 6 and 12 months. A 3-month blanking period will be applied after the index procedure, during which early recurrences of AF/AT will not be counted.

All patients will be required to perform a 24-hour Holter prior or subsequent to each in-office visit at 3, 6 and 12 months post-procedure. The 24-hour Holter recording must be performed within the same time windows as the in-office visit specified in Table 8.

At each in-office visit (3, 6 and 12 months or unscheduled follow-up visit), the following assessments/procedures will be performed:

- Diagnostic 12-lead ECG
- Assessment of Holter report if available (only during scheduled visits)
- QoL questionnaires (only during scheduled visits)
  - It is recommended that QoL questionnaires be completed prior to any other follow-up procedures in order to reduce influencing the subject's responses.
- Concomitant cardiac medications
- Adverse event documentation

At the 12-month visit, a blinding assessment should be done by asking the subject which arm of the study they believe they are in. The subject's response should be recorded.

If AF and/or AT recurrences are observed during follow-up, further treatment shall be at the discretion of the physician (e.g. drugs or re-ablation or cardioversion). Re-ablations after the 3 months blanking period and before the end of the 9th month after the first procedure are highly recommended.

In the event of aggravating circumstances (new Covid-19 outbreak), these visits can be carried out remotely.

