Ziiapoiiii(o)	2. Freedom from documented AF/AT, after one procedure, with or
	without AADs, at 12 months
	·
	· · · · · · · · · · · · · · · · · · ·
	serious treatment-related adverse event at 12 months after index
	procedure.

Exploratory Endpoints

- 1. Freedom from documented AF, after one or two procedures, with or without AADs, at 12 months
- 2. Freedom from documented AF or AF/AT, after one procedure, or one procedure or more, without AADs, at 12 months
- 3. Freedom from documented AF or AF/AT, after one procedure, or one procedure or more, without AADs or with previously failed AAD at the same dose, at 12 months
- 4. Freedom from documented AF or AF/AT, after one procedure, or one procedure or more, with or without AADs, at 12 months, without the use of TTM
- 5. Freedom from documented symptomatic AF or AF/AT, after one procedure, or one procedure or more, with or without AADs, at 12 months
- Freedom from AF or AF/AT, with or without AADs, 12 months after one procedure, or one procedure or more, for subjects with persistent AF <1 year
- 7. Quality of life measurements (SF-36 and AFEQT) at baseline, 3, 6 and 12 months post-index procedure
- 8. Incidence of peri-procedural complications including stroke, PV stenosis, cardiac perforation, esophageal injury, and death
- 9. Acute AF termination rate by ablation
- 10. Rate of conversion to sinus rhythm by ablation
- 11. Ablation procedure duration
- 12. Fluoroscopy time and dose
- 13. Mapping time
- 14. Radiofrequency (RF) time to terminate AF
- 15. Total RF time
- 16. Total delivered energy (mean power x RF duration)
- 17. Total delivered energy (mean power x RF duration) / biatrial surface
- 18. Ablation surface area to terminate AF
- 19. Total ablation surface area
- 20. Blinded baseline Voltage maps before ablation
- 21. TTM compliance (% of transmissions expected vs received at each week post index procedure)
- 22. Assessment of blind maintenance per group

Follow-Up Schedule

Follow-up assessments at 3, 6, and 12 months post index procedure. Holter and 12-lead ECGs will be performed at 3, 6, and 12 months. Portable trans telephonic event monitors will be recorded weekly for approximately 52 weeks.

2 Abbreviations

AAD	Antiarrhythmic Drug
ADE	Adverse Device Effect
AE	Adverse Event
AF	Atrial Fibrillation
AFEQT	AF Effect on Quality-of-Life Questionnaire
AT	Atrial Tachycardia
СР	Conditional Power
ECG	Electrocardiogram
HR	Hazard Ratio
mITT	Modified Intention-To-Treat
PP	Per-Protocol

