6.2 BLANKING PERIODS

After the index procedure, a 3-month blanking period + tolerance of 1 week (98 days) will be applied for all efficacy endpoints, during which recurrences of AF/AT (excluding repeat procedure) will not be counted.

If a repeat procedure is performed during the 3-month blanking period (and patient is in spontaneous AF), the recurrence and the repeat procedure will be counted as occurring at 3 months.

If a repeat procedure is performed after the end of the 9th month, the procedure will not be considered for multiple procedures endpoints.

After a repeat procedure, a 2-week blanking period (14 days) will be applied, during which AF/AT recurrences will not be counted. Any re-repeat procedures (repeat procedure #2) will result in the data being censored at the time of the re-repeat procedure.

Note: for the purpose of counting months to establish blanking period boundaries in the study, one month will be considered equal to 30.4 days.

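### SAP 4.4.1 puts AF burden (endpoint 8) under a Cox model that cannot be run on it, and no formula for burden is given; a lesser point is that yes/no endpoints 10-12 get a test of means with no planned risk difference

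*SAP*

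**What the plan says.** SAP 4.4.1 assigns methods by endpoint number: "Endpoints 1-8 will be tested using a Cox proportional hazards model with randomization group and AF strata as fixed effects". Endpoint 9 (quality of life) gets a t-test at each visit with a Wilcoxon-type fallback, plus a mixed model for the effect of time. Endpoints 10 to 21 and 23 get a t-test for means; if normality fails, a non-parametric method replaces it, with Wilcoxon named as an example.

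Item 8 of the SAP 4.4 list is "Estimated AF or AF/AT burden, with or without AADs, after one procedure, or one procedure or more". Items 10 to 12 are the incidence of peri-procedural complications, the AF termination rate and the rate of conversion to sinus rhythm.

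The only description of burden is a footnote to Table 4 in protocol 4.3: "Post-ablation arrhythmia burden is estimated based on TTM and/or Holter recordings". Patients are asked for "one 30-second ECG recording per week, and whenever they have arrhythmia symptoms" (protocol 5.3.5). SAP 6.2 applies a "3-month blanking period + tolerance of 1 week (98 days) will be applied for all efficacy endpoints".

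Protocol 6.5.2 applies log-rank tests to survival data, which it identifies as endpoints 2-9. It gives t-test or Wilcoxon for continuous measures, chi-square or Fisher for categorical data, and a mixed model for the difference between arms in quality of life. SAP section 3 makes the SAP prevail over the protocol. SAP section 7 lists two changes, the primary hypothesis and the dropped gatekeeping, and neither concerns these methods.

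**The concern.** A Cox model needs, for each patient, a time to an event and an indicator of whether it was observed. Burden is an amount of arrhythmia and supplies neither, and no surrogate event is defined. The analyst would have to replace both the method and the outcome definition, and if that happens after arm-level results are visible, the comparison is no longer pre-specified.

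For endpoints 10-12 the natural summary is a difference in proportions with its confidence interval. A rank test on yes/no data does not give one. The protocol had a categorical test for these endpoints, and the SAP replaces it without recording the change.

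**Working it through.** **1. Which item is endpoint 8?** The SAP has two exploratory lists. Section 1 omits burden and has "7. Quality of life measurements (SF-36 and AFEQT) at baseline, 3, 6 and 12 months post-index procedure"; section 4.4 has burden at 8 and quality of life at 9. Section 4.4.1 treats quality of life as endpoint 9 and says "Endpoint 22 will not undergo any statistical analysis, but the data collected (blinded baseline voltage maps prior to ablation"; the voltage maps are item 22 in section 4.4 and item 20 in section 1. So 4.4.1 follows the 4.4 list, and endpoint 8 is burden.

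**2. Did the protocol treat burden as survival data?** In Table 4 burden is endpoint 12, outside the range 2-9. Protocol 6.5.2 numbers quality of life as 10 where Table 4 has 13, so its numbering is not fully aligned. Even so, the log-rank rule is for survival data, Table 4 items 5 to 9 are all freedom-from-arrhythmia outcomes, and 6.5.2 nowhere treats burden as survival data.

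**3. How far does the missing formula matter?** The window can be derived from the 98-day blanking and 12 months of follow-up.
- Weekly strips: (365 - 98)/7 = 38.1, so about 38 strips x 0.5 min = 19 min, if all are received.
- Holters: the "24-hour Holter recording must be performed within the same time windows as the in-office visit specified in Table 8". The 3-month window closes at 3 months (3 x 30.4 = 91 days), inside the blanking. That leaves the 6- and 12-month Holters: 2 x 1,440 = 2,880 min.
- TTM share of recorded time: 19/2,899 = 0.7%. Share of recordings: 38/40 = 95%.

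Assumed patient with AF on 4 strips and on neither Holter:

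| Formula | Burden |
|---|---|
| Share of strips | 4/38 = 10.5% |
| Share of recordings | 4/40 = 10.0% |
| Share of recorded time | 2/2,899 min = 0.07% |
| Share of strips, with 6 added symptom-triggered AF strips | 10/44 = 22.7% |

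**4. Shape of the burden data.** If patients free from AF have zero burden, the planning rates of 62% and 77% imply that 0.62 x 0.77 = 48% of between-arm pairs tie at zero. A rank test alone would then say little about the size of any difference.

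**5. Endpoints 10-12.** The documents give no complication rate, so the counts are assumed. Two-sided p-values at 146 per arm:

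| Events | t-test | Wilcoxon | Chi-square | Fisher |
|---|---|---|---|---|
| 4 v 0 | 0.044 | 0.044 | 0.044 | 0.122 |
| 5 v 0 | 0.024 | 0.024 | 0.024 | 0.060 |

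At 187 per arm, 5 v 0 gives 0.024 by t-test and chi-square, 0.025 by Wilcoxon and 0.061 by Fisher.

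Exact type I error at nominal two-sided 0.05, by binomial enumeration at 146 per arm for true rates of 0.5% to 10%, is 0.006 to 0.049 for the t-test, with Wilcoxon the same to 0.0001. At a true rate of 30% both give 0.050.

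The estimate that is not planned would be, for 5 v 0, 5/146 = +3.4% with Newcombe 95% CI 0.2% to 7.8%.

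A Shapiro-Wilk test on 146 yes/no values with 1 to 73 events gives p below 1e-16, so these endpoints always leave the t-test for the fallback.

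**6. Quality of life.** Half-width of the 95% CI in SD units is 1.96 x sqrt((2/146) x (1 - rho^2)), where rho is the correlation with baseline. For rho = 0, 0.4 and 0.6 it is 0.229, 0.210 and 0.184. The values of rho are assumptions.

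**The case against.** The range 1-8 may simply be a slip for 1-7: the first seven items are all freedom-from-arrhythmia outcomes, burden is the next one, and nobody is likely to fit the model as written. That is plausible, and it makes the correction trivial, but it does not supply the missing formula, which is the substantive gap.

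On endpoints 10-12 the other side is stronger. A reader might infer that a t-test or Wilcoxon on yes/no data gives false positives; the enumeration shows no inflation. A reader might blame the SAP's tests for the gap between 0.024 and 0.060; that gap is chi-square against Fisher, and protocol 6.5.2 offers both with no rule for choosing, so restoring its wording alone would leave the gap in place. A reader might also infer that the plan forces Wilcoxon; the SAP names it only as an example, so the wording does not rule out an exact test. SAP 4.5.1 further says that proportions of subjects with events will be reported and that acute complications within one week of ablation will be analysed. What stands is that no categorical test is named for these endpoints and no between-arm difference with interval is planned.

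The visit-wise quality-of-life comparison should not be read as an error: a t-test with a rank fallback is valid. Using the mixed model for the arm comparison is only an improvement.

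**Conclusion.** The burden analysis cannot be carried out as SAP 4.4.1 is written, and its outcome is undefined beyond the data source. The choice of formula can move one patient's figure from 10.5% to 0.07%. That example assumes complete weekly transmission and an invented AF pattern, so it shows sensitivity and is not a forecast.

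The yes/no endpoints are a lesser matter. The p-values nearly coincide with chi-square; the practical loss is a planned risk difference with interval and a named exact test for sparse complications. The event counts used are assumptions.

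All the endpoints are exploratory. It would be wrong to infer any effect on the primary result, the sample size or the composite safety endpoint, which has its own methods in SAP 4.5. Nor do the documents show that data collection or unblinding has taken place, so it cannot be said that the burden formula has been or will be chosen with results in view. The change should be made because it is cheap and one planned analysis is otherwise unworkable.

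**What to change.** Amend the SAP before unblinding; if arms have already been unblinded, label the changes post hoc.

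- **Cox model:** limit it to endpoints 1-7, and align the section 1 list with section 4.4.
- **Burden:** define it per patient as the share of received scheduled weekly TTM strips in AF (or AF/AT) after the 98-day blanking, excluding symptom-triggered strips, with Holter burden reported separately. For one-procedure burden, stop at the redo. For multiple-procedure burden, apply the 14-day post-redo blanking and censor at a third procedure, as in SAP 6.2. State a minimum number of received strips. Compare arms by Wilcoxon, and report the share with zero burden and the mean difference with a bootstrap CI.
- **Endpoints 10-12:** use chi-square, or Fisher when any expected cell count is below 5. With equal arms that means fewer than 10 events in total, so 4 v 0 and 5 v 0 would go to Fisher. Report the risk difference with 95% CI, in line with the proportions in SAP 4.5.1.
- **Quality of life (optional improvement):** use the planned mixed model with arm, visit, arm-by-visit and baseline score for the arm comparison.
- **SAP section 7:** list any remaining departure from protocol 6.5.2.

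The cost is SAP wording and minor programming, on data that the protocol already plans to collect.

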#### 6.5.2 – Other secondary and exploratory endpoints

For all other survival data, one-sided and two-sided Log-Rank test will be applied at a significance level of 0.05 (secondary/exploratory endpoints 2-9). The secondary efficacy endpoints will be evaluated in a pre-specified order following a gatekeeping approach so that subsequent endpoints will be evaluated if and only if the previous endpoint was found to achieve statistical significance. Thus, no correction for multiple testing will be required. Further details including the ordering of endpoints will be provided in the statistical analysis plan (SAP).

For quality of life (endpoint 10), a linear mixed model for repeated data will be used to examine the difference between groups over time.

For all other endpoints:

The continuous variables will each be analyzed by a Student's t-test, and equivalent non-parametric method, the Wilcoxon–Mann–Whitney test, will be used in case of violation of the normality assumption. Chi-square test or Fisher exact test will be used for the categorical data.

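### Quality of life: the SAP's between-arm test is a t-test at each visit without baseline adjustment, and the mixed model it keeps has no stated arm contrast, unlike the protocol's

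*SAP*

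**What the plan says.** SAP 4.4 lists, among endpoints it calls exploratory, "Quality of life measurements (SF-36 and AFEQT) at baseline, 3, 6 and 12 months post-index procedure" (endpoint 9 there).

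SAP 4.4.1 sets the between-arm test: "Endpoint 9 will be tested by comparing the QoL score at each visit between tailored and anatomical ablation using a t-test". A Shapiro-Wilk test checks normality, and then: "Should the normality assumption be violated, a non-parametric method such as the Wilcoxon test will be used instead". The paragraph ends: "The effect of time will also be assessed using a generalized linear mixed model for repeated measures". It names no baseline covariate, key visit, key score or significance level for this endpoint. The one-sided 0.05 level in that section is written for endpoints 1 to 8.

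Protocol 6.5.2 gives quality of life its own method: "a linear mixed model for repeated data will be used to examine the difference between groups over time". It keeps the t-test and the Wilcoxon test for the remaining endpoints. (It calls quality of life endpoint 10; Table 4 of the protocol numbers it 13.)

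SAP Section 3 says that the SAP prevails where the two documents differ. SAP Section 7 lists two changes from the protocol: the primary hypothesis, and the abandoned gatekeeping for secondary endpoints. The quality-of-life method is not among them.

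**The concern.** The protocol's question is how the arms differ over time, and it answers it with a repeated-measures model. The SAP moves the between-arm comparison to separate tests of raw scores. Three things are lost.

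- **Precision.** The baseline score usually predicts the follow-up score. It is collected on every patient under the plan and then left out of the treatment comparison. Any chance difference between arms at baseline also passes partly into the follow-up difference.
- **Partial follow-up.** A test at one visit uses only the forms returned for that visit. A patient with forms at 3 and 6 months but not at 12 contributes nothing to the 12-month comparison.
- **A fixed target.** The pre-test decides whether the result is a difference in means or a rank comparison, so the reported quantity depends on the data.

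SAP Section 3 allows the specified analyses to be used in manuscripts and regulatory submissions. Protocol 7.3 expects longer RF times, a greater ablation area and slightly longer procedures in the Tailored arm. A well-estimated quality-of-life difference would help weigh benefit against that burden.

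**Working it through.** **Figures in the documents.** Neither document gives a sample size, power, standard deviation or effect size for quality of life, so there is no figure of its own to reproduce. The evaluable number, 146 per arm (Protocol 6.2, SAP 4.2.2), comes from the primary endpoint. It reproduces: HR = ln(0.77)/ln(0.62) = 0.547, and a log-rank calculation with exponential survival, 12 months of follow-up and one-sided 0.025 gives 80.0% power at 292 patients. I use 146 per arm below only for scale.

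**Precision.** The baseline-to-follow-up correlation rho is assumed; it is not in the documents. Adjusting for baseline multiplies the variance of the arm difference at a visit by 1 − rho², and the standard error by √(1 − rho²). The equivalent gain in patients is 1/(1 − rho²) − 1. The difference detectable with 80% power at two-sided 0.05 (level assumed), in SD units, is (1.960 + 0.842) × √(2(1 − rho²)/146). Without adjustment this is 2.802 × 0.117 = 0.328 SD.

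| rho (assumed) | 1 − rho² | SE factor | SE lower by | Equivalent extra patients | Detectable difference (SD) |
|---|---|---|---|---|---|
| 0.3 | 0.91 | 0.954 | 4.6% | 10% | 0.313 |
| 0.4 | 0.84 | 0.917 | 8.3% | 19% | 0.301 |
| 0.5 | 0.75 | 0.866 | 13.4% | 33% | 0.284 |
| 0.6 | 0.64 | 0.800 | 20.0% | 56% | 0.262 |

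**Baseline imbalance.** The standard error of a chance baseline difference is √(2/146) = 0.117 SD. An imbalance of that size carries rho × 0.117 into the unadjusted follow-up difference: 0.035 SD at rho 0.3 and 0.070 SD at rho 0.6. An imbalance of 0.2 SD is 0.2/0.117 = 1.7 standard errors, reached in about 9% of trials in either direction, and would carry 0.06 to 0.12 SD.

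**Why one contrast should be named.** Suppose each test were read at two-sided 0.05. One score over three post-baseline visits gives a chance of at least one false positive of 1 − 0.95³ = 14.3% if the tests are independent. A simulation with between-visit correlation 0.3 to 0.7 gives 11% to 14%. For two scores, one per instrument, the figures are 1 − 0.95⁶ = 26.5% if independent, and 19% to 24% with those correlations and 0.5 assumed between scores. The SAP does not say how many SF-36 scores will be tested.

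**The two mixed models.** The protocol's model has a stated target, the group difference over time. The SAP's model has a stated target of time, with no arm term, arm-by-visit term, baseline term or covariance structure. The SAP wording neither includes nor excludes an arm contrast, so it cannot be assumed to deliver the protocol's comparison.

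**The case against.** The strongest defence is that the endpoint is exploratory in both documents, carries no power or claim, and is analysed validly. With complete data, randomisation makes an unadjusted t-test unbiased, and nothing here affects the primary test. That stands, and it limits the weight of the point.

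A second defence is that the SAP has not discarded the mixed model. This also stands. A reader might infer from the t-test sentence that the protocol's model was dropped, but the same paragraph retains a repeated-measures model, introduced as an additional assessment. What can be said is that its arm contrast and baseline term are not stated, and that the test named for comparing the arms is the t-test.

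Three further readings are tempting and not supported:

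- **That 22% of forms will be missing.** Protocol 6.2 and SAP 4.2.2 define the 22% to include patients who never have an ablation. Those patients, and patients lost during the blanking period, are outside the mITT set. No missing-form rate appears in either document. Patients with no post-baseline form would add nothing to a model with baseline as a covariate.
- **That a between-arm test at baseline is planned.** SAP 4.4 lists a baseline measurement, so a test at every visit could include it. Protocol 5.3.6, however, uses scheduled in-office visits for months 3, 6 and 12. It is one reading only.
- **That the gain is worth 56% more patients.** That is the favourable end of an assumed range; at rho 0.3 the figure is 10%.

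**Conclusion.** The point holds as an avoidable loss of precision and an unrecorded change of method on an exploratory endpoint. It is not an invalid analysis. Baseline adjustment would lower the standard error by about 5% to 20%, if the baseline-to-follow-up correlation lies between 0.3 and 0.6. That range is an assumption.

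The benefit from using partial follow-up cannot be sized from the documents. It also rests on forms being missing at random given the observed scores. The false-positive figures assume a two-sided 0.05 reading that the SAP does not state for this endpoint. They support naming one contrast and do not show that any planned claim is at risk. The correction is worth making because it uses data already collected and costs almost nothing.

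**What to change.** In SAP 4.4.1:

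1. Make one mixed model for repeated measures per score the main between-arm analysis. Use the baseline score as covariate, arm, visit and arm-by-visit as fixed effects, and an unstructured covariance.
2. Name one score per instrument. Report its adjusted 12-month difference with a two-sided 95% confidence interval as the key contrast, and give months 3 and 6 as supportive estimates.
3. Remove the Shapiro-Wilk switch and state that no between-arm test is done at baseline.
4. Say how a missing baseline form is handled.

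In SAP Section 7, record the change of method from Protocol 6.5.2.

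The cost is a few lines of SAP text and some programming. No new data, visits or patients are needed.
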